8.2.2. Secondary Efficacy Endpoint(s) and Analyses

The secondary efficacy endpoints include mean seated office SBP, and mean ambulatory and seated office DBP. No adjustment for multiple comparisons will be applied.

8.2.2.1. The placebo-adjusted change from week 12 to week 24 in seated office SBP

A summary and analyses will be provided as in section 8.2.1.1. The model will include baseline seated office SBP in place of baseline mean ambulatory SBP.

8.2.2.2. The placebo-adjusted change from week 12 to week 24 in mean ambulatory DBP from week 12 to week 24

A summary and analyses will be provided as in section 8.2.1.1. The model will include baseline mean ambulatory DBP in place of baseline mean ambulatory SBP.

8.2.2.3. The placebo-adjusted change from week 12 to week 24 in seated office DBP

A summary and analyses will be provided as in section 8.2.1.1. The model will include baseline seated office DBP in place of baseline mean ambulatory SBP.

8.2.3. Exploratory Endpoints and Analyses

8.2.3.1. The proportion of subjects requiring any rescue medication at week 24

Subjects who require any rescue medication will be summarized using frequency and percentage by treatment arm. Logistic regression will be used to analyze the treatment effect. The model will include the rescue medication/response as assessed by ABPM SBP at baseline (Week 12) (i.e., require rescue medication, not require rescue medication: SBP change ≤ 5 mmHg, $> 5 - \leq 20$ mmHg, > 20 mmHg), baseline ABPM SBP value, and randomized treatment for study 603B as fixed effects. LS Mean responding proportion and 95% CI will be estimated within each treatment group from the logistic regression model. P-value for comparison of treatment group will also be provided.

8.2.3.2. The placebo-adjusted change from week 12 to week 24 in 24-hour ABPM SBP by response status

The effect of withdrawal will be studied for each subgroup of subjects separated by their response status at baseline week 12 (i.e., require rescue medication, not require rescue medication: SBP change ≤ 5 mmHg, $> 5 - \leq 20$ mmHg, > 20 mmHg, and > 5 mmHg). A summary and analyses will be provided as in section 8.2.1.1 for subjects in each group. Baseline ABPM SBP value will be used as covariate and the randomized treatment will be included as the fix effects in the model.

8.3. INTEGRATED ANALYSES

Assessments for studies 603A and 603B will be combined to further assess the effectiveness of bexagliflozin after treatment for 12, 24, and 36 weeks. The sequence numbers in this section refer to the numbers in Table 2. All analyses will be based on the integrated ITT analysis set.

8.3.1. Change in mean ambulatory SBP or DBP after 12, 24, and 36 weeks of treatment of bexagliflozin

Summary statistics will be provided for actual value at baseline, and actual value and change from baseline after 12, 24, and 36 weeks treatment with bexagliflozin. The 95% CI based on normal distribution will also be presented for the change value. For subjects who require rescue medication, the ABPM taken prior to rescue medication (as was used for the primary analyses for studies 603A and 603B) for the time point will be used.

The proportion of subjects who achieve defined goals will be summarized after 12, 24, and 36 weeks treatment with bexagliflozin using frequency, percentage and 95% binomial confidence interval. These goals will include:

- A reduction of mean ambulatory SBP of 10 mm Hg or greater;
- A reduction of mean ambulatory DBP of 4 mm Hg or greater.

8.3.2. Change in seated office SBP or DBP after 12, 24, and 36 weeks treatment of bexagliflozin

Summary statistics as in section 8.3.1 will be provided for seated office SBP or DBP. The proportion of subjects who achieve defined goals will be summarized after 12, 24, and 36 weeks treatment with bexagliflozin using frequency, percentage and 95% binomial confidence interval. These goals will include:

- The proportion of subjects who achieve a mean seated office SBP of 140 mm Hg or less at week 12.
- The proportion of subjects who achieve a mean seated office DBP of 90 mm Hg or less at week 12.

8.3.3. Cumulative mean change from baseline in seated office SBP and DBP as a function of time (including all scheduled office visits) for subjects exposed to bexagliflozin

Summary tables will be presented for seated office SBP and DBP by treatment sequence for all subjects in 603B ITT population. Table will include baseline, actual value and change from baseline at cumulative weeks 6, 12, 18, 24, and 36. Baseline is defined as the last non-missing value before the first dose of bexagliflozin in 603A. A by-sequence plot of change from baseline will include mean and standard error.

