## **Guidance for Hypertensive Rescue Medication Use**

### Study 603A, cumulative weeks 1-6

- Follow procedures for visits 10 and 11 as early termination visits to obtain 24-h ABPM and collect safety data
- Rescue medication should not be administered unless hypertensive emergency appears imminent. In those situations, refer the subject to seek urgent care in a clinic or hospital. Subject should withdraw from participation in the study and see primary care provider to start or intensify anti-hypertensive therapies

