3.3. INTEGRATIVE OBJECTIVES OF STUDY 603A AND 603B

- To assess consistent effects on mean ambulatory SBP/DBP after 12 weeks of bexagliflozin treatment, as well as longer treatment periods, i.e., 24 weeks or 36 weeks of bexagliflozin treatment.
- The seated office systolic and diastolic blood pressure will be collected at more frequent intervals than for ambulatory monitoring, and the changes over time will be evaluated to provide a composite profile of treatment effect as a function of time.

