4.3. INTEGRATED ANALYSES

Assessments for studies 603A and 603B will be combined to further assess the effectiveness of bexagliflozin after treatment of 12, 24, and 36 weeks.

There are four (4) separate treatment sequences after combining studies 603A and 603B (Table 2).

Table 2 Treatment Sequences for combined studies 603A and 603B

Sequence	Period 1	Period 2	Period 3
Seq 1 PBB	(603A) placebo	(603B) bexagliflozin	(603B) bexagliflozin
Seq 2 PBP	(603A) placebo	(603B) bexagliflozin	(603B) placebo
Seq 3 BBB	(603A) bexagliflozin	(603B) bexagliflozin	(603B) bexagliflozin
Seq 4 BBP	(603A) bexagliflozin	(603B) bexagliflozin	(603B) placebo

The following secondary endpoints will be assessed:

- Change in mean ambulatory SBP or DBP after 12 weeks treatment with bexagliflozin using week 12 assessments for Seq 3 or 4 (end of Period 1) and cumulative week 24 assessments for Seq 1 or 2 (end of Period 2);
- Change in mean ambulatory SBP or DBP after 24 weeks treatment with bexagliflozin using cumulative week 24 assessments for Seq 3 or 4 (end of Period 2) and cumulative week 36 assessment of Seq 1 (end of Period 3);
- Change in mean ambulatory SBP or DBP after 36 weeks treatment with bexagliflozin using cumulative week 36 assessments for Seq 3 (end of Period 3);
- Change in seated office SBP or DBP after 12 weeks treatment with bexagliflozin using week 12 assessments for Seq 3 or 4 (end of Period 1) and cumulative week 24 assessments of Seq 1 or 2 (end of Period 2);
- Change in seated office SBP or DBP after 24 weeks treatment with bexagliflozin using cumulative week 24 assessments for Seq 3 or 4 (end of Period 2) and cumulative week 36 assessments for Seq 1 (end of Period 3);
- Change in seated office SBP or DBP after 36 weeks treatment with bexagliflozin using cumulative week 36 assessments for Seq 3 (end of Period 3).
- Cumulative mean change from baseline in seated office SBP as a function of time (including all scheduled office visits) for subjects exposed to bexagliflozin
- Cumulative mean change from baseline in seated office DBP as a function of time (including all scheduled office visits) for subjects exposed to bexagliflozin

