5.1.2. Study 603B

- ITT Analysis Set: will include all subjects who are randomized at week 12. All subjects will be analyzed according to the treatment to which they were randomized to receive.
- Safety Analysis Set: will include all subjects who have taken at least one dose of investigational product.
- Safety Analysis Set for withdrawal period: will include all subjects who are randomized at week 12 and have taken at least one dose of double blind investigational product. All subjects will be analyzed according to the treatment they receive.

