5.1.3. Integrated Analyses

- Integrated ITT Analysis Set: will include all subjects who are randomized to bexagliflozin in 603A, or entered study 603B run-in period. The set will include all subjects to whom a study kit is dispensed in 603B run-in period, and subjects who are randomized to bexagliflozin in 603A.
- Integrated Safety Analysis Set: will include all subjects who are treated with at least one dose of bexagliflozin in either study. This will include subjects in the 603B safety analysis set and subjects who received at least one dose of bexagliflozin during 603A.

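### SAP 8.3.3 limits the seated office blood pressure profile, from cumulative week 6 on, to subjects re-randomized after cumulative week 24, against the population rule in SAP 8.3

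*SAP*

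**What the plan says.** SAP 3.3 sets an integrative objective for seated office pressure, which is collected more often than ambulatory pressure: "to provide a composite profile of treatment effect as a function of time". SAP 4.3 lists the cumulative mean change in seated office SBP and DBP among the integrated secondary endpoints.

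SAP 8.3 opens with a general rule: "All analyses will be based on the integrated ITT analysis set". SAP 5.1.3 defines that set: "Integrated ITT Analysis Set: will include all subjects who are randomized to bexagliflozin in 603A, or entered study 603B run-in period". It does not require a second randomization.

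SAP 8.3.3, under a heading that refers to subjects exposed to bexagliflozin, uses another population: "Summary tables will be presented for seated office SBP and DBP by treatment sequence for all subjects in 603B ITT population". It goes on: "Table will include baseline, actual value and change from baseline at cumulative weeks 6, 12, 18, 24, and 36". SAP 5.1.2 defines the 603B population: "ITT Analysis Set: will include all subjects who are randomized at week 12". Week 12 of 603B is cumulative week 24, and the second randomization takes place at Visit 9, one day later.

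SAP 8.3.3 takes as baseline the last value before the first bexagliflozin dose in 603A. SAP Section 12, which lists departures from the protocol analysis, mentions neither the population nor this baseline.

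**The concern.** Cumulative weeks 6, 12, 18 and 24 all precede the event that admits a subject to the 603B ITT set. Anyone who leaves before re-randomization is removed from visits that he or she may well have attended.

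Some of those exits are related to blood pressure. For the rescue criterion in weeks 1 to 6, Protocol 3.1.3 says: "Subject should withdraw from participation in the study and see primary care provider". SAP 8.1.1.2 likewise says that rescue started in that window ends participation. A missing mean ambulatory SBP at cumulative week 24 also leads to withdrawal (Protocol 5.4, SAP 3.8.1). SAP 6.4 allows early-termination values to stand in for missing scheduled visits in efficacy analyses, so usable office readings may exist for subjects whom the population choice discards.

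At stake is the one planned display of seated office pressure across all scheduled office time points of both studies. SAP 8.3.2 covers only 12, 24 and 36 weeks of exposure. The by-visit 603A summaries end at week 12. The integrated vital-signs summary in SAP 9.5 covers supine, standing and orthostatic pressure, not seated pressure. In addition, the placebo-first and bexagliflozin-first lines at weeks 6 and 12 would not be the groups formed by the first randomization.

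**Working it through.** **Planning figures (Protocol 9.2, SAP 3.7).** Inputs for 603B: difference 4 mm Hg, SD 15 mm Hg, two-sided alpha 0.05, power 85%.

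- n per arm = 2 × 15² × (1.960 + 1.036)² / 4² = 252.5, so 253; the plan says 254.
- 2 × 254 / 0.75 = 677.3, so 678; the plan says 680.
- 680 × 0.92 = 625.6, so 626; the plan says 626.

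The attrition figures reproduce within rounding and can be used.

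**Size of the 603B ITT set.** The plan gives no retention at cumulative week 24. It must lie between the week-12 and week-36 figures.

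| Assumption for week 24 | Retained | Outside the cohort |
|---|---|---|
| No loss after week 12 (92%) | 626 | 680 − 626 = 54 (8%) |
| Linear between weeks 12 and 36: (0.92 + 0.75)/2 = 0.835 | 568 | 112 (16.5%) |
| Constant hazard: √(0.92 × 0.75) = 0.831 | 565 | 115 (17%) |
| All loss before week 24 (75%) | 680 × 0.75 = 510 | 170 (25%) |

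These counts are of all randomized subjects. Some of them will have no reading at a given visit. If all 626 subjects expected at week 12 have an office reading, the week-12 readings discarded number 626 − 626 = 0 to 626 − 510 = 116, and 58 to 61 on the two interpolations.

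**Against the rule in SAP 8.3.** With equal dropout in the two arms, the integrated ITT set holds 340 bexagliflozin-first subjects plus 340 × 0.92 ≈ 313 placebo-first subjects who enter 603B, 653 in all. SAP 8.3.3 therefore drops 653 − 626 = 27 to 653 − 510 = 143 subjects (4% to 22%) whom SAP 8.3 would keep. The integrated ITT set would itself lack 340 − 313 = 27 placebo subjects at weeks 6 and 12, so substituting it would not fully restore the randomized groups.

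**What a shift could look like (assumption only).** Shift in an early mean = share excluded × (mean change in the excluded − mean change in the retained). For excluded shares of 8% to 25% of 680:

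- gap of 2 mm Hg: 0.16 to 0.50 mm Hg
- gap of 5 mm Hg: 0.40 to 1.25 mm Hg
- gap of 10 mm Hg: 0.79 to 2.50 mm Hg

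The documents give no such gap, and no sign for it.

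**Baseline.** Placebo-first subjects take no bexagliflozin in 603A, so the baseline in SAP 8.3.3 does not exist for them. The integrated baseline in SAP 6.2.1 does exist: it is the last value before the 603B run-in dose. For these subjects, however, it falls after the week-6 reading and at about the time of the week-12 reading, so it cannot serve a profile that starts at week 6.

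**The case against.** The strongest defence is that a fixed cohort has a real virtue: its trend from week 6 to week 24 cannot be produced by subjects leaving. A line built on whoever has data at each visit has a changing denominator and can drift for that reason alone. This stands, and is why the 603B ITT view should be kept as a supplement. It does not justify making that view the only one, or leaving it in conflict with SAP 8.3.

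Second, less selected results exist. The week-12 office comparisons use the 603A ITT set with last observation carried forward (SAP 8.1, 8.1.2), and SAP 8.3.2 summarizes office pressure after 12, 24 and 36 weeks of exposure. SAP 8.3.3 specifies no test between lines. This also stands, and limits the consequence to a descriptive display.

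Third, a reader might infer that the early results are made to look better than they are. The documents do not support that. Only rescue in weeks 1 to 6 ends participation. Subjects who meet the criterion in weeks 7 to 12 move into 603B, those rescued later continue, and subjects rescued before week 24 form one of the four groups balanced at the second randomization. Reasons for dropout are not projected, and withdrawals for hypotension could act the other way. The placebo-first lines are selected as well, so the gap between lines could move in either direction. Nor can the illustrative shifts be set against the planned 5 mm Hg, which is a placebo-adjusted ambulatory difference.

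Fourth, a reader might infer that the 12-week integrated endpoints carry the same restriction, because SAP 4.3 words them by sequence: "using week 12 assessments for Seq 3 or 4 (end of Period 1". They do not. SAP 8.3.1 and 8.3.2 fall under the integrated ITT rule. Sequences 3 and 4 together can be read as the 603A bexagliflozin arm. The baseline rule in SAP 6.2.1 is first stated without sequence labels. This is loose wording, not a population restriction.

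**Conclusion.** The point holds for SAP 8.3.3 alone. The section contradicts the population rule that opens SAP 8.3, does not match its own heading, and conditions four of its five time points on reaching a later randomization. Between 54 and 170 of 680 subjects (8% to 25%) fall outside the cohort, about 17% by interpolation. These counts rest on the plan's own 92% and 75% retention figures and on no others. Among those left out are subjects whose participation ended because of rescue in weeks 1 to 6.

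The direction and size of any resulting bias are unknown; every mm Hg figure above depends on an assumed gap. No primary test is affected, and the 12-week endpoints in SAP 8.3.1 and 8.3.2 are not restricted in this way. The change is still worth making, because the profile is a listed secondary endpoint and its early points will differ with the population used.

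**What to change.** 1. In SAP 8.3.3, present cumulative weeks 6 to 24 by 603A arm (two lines) on all 603A-randomized subjects with data at the visit, and show n at each visit. Until the second randomization, the two placebo-first sequences receive the same treatment, as do the two bexagliflozin-first sequences. Four lines only halve the n per line there.
2. Split into the four sequences only after cumulative week 24, on the 603B ITT set.
3. Keep the fixed 603B ITT cohort over all visits as a labelled supplementary view, because the available-data lines have a changing denominator.
4. For this cumulative profile, define baseline for every subject as the last value before the first double-blind dose in 603A, and state that it differs from the exposure-based baseline in SAP 6.2.1.
5. State in SAP 8.3 that SAP 8.3.3 is an exception to the integrated ITT rule, and give the reason.
6. As a wording tidy-up in SAP 4.3 and 6.2.1, wherever the time point precedes the second randomization, replace the labels Seq 3 or 4 and Seq 1 or 2 with the 603A bexagliflozin arm and the 603A placebo subjects who entered 603B.

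The cost is SAP wording and one table and figure shell, with the supplementary view as a repeat of that output. No new data are needed.

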9. SAFETY

All analyses described in this section will be performed separately for each study and integrated analysis. The analysis set used for safety analyses will be the safety analysis

set for 603A, safety analysis set for withdrawal period for 603B, safety analysis set for 603B run-in period, and integrated safety analysis set for integrated analysis. Safety data include AEs; physical examination results; vital signs, including blood pressures; ECG results; and clinical laboratory results, including serum chemistry, hematology, serum lipids, and urinalysis.

9.1. EXTENT OF EXPOSURE

Study drug exposure will include:

- Treatment duration by treatment group
- Total dose received by treatment group

Treatment duration (in weeks) is calculated as (the date of the last dose of study drug - the date of the first dose of study drug + 1) / 7 and rounded to 1 decimal place. Total dose consumed will be calculated as number of tablets dispensed on the first day after randomization - number of tablets returned on the last day of the period. If any of the bottles dispensed are not returned, it will not be possible to compute the total dose consumed. In this case, the number of tablets consumed will be considered as missing.

Exposure will be summarized for study 603A, 603B, and integrated.

Summary statistics for treatment duration (in weeks) and total dose consumed, as well as a frequency summary of treatment duration categories (e.g., < 1, 1 - < 3 weeks), will be provided.

9.2. TREATMENT COMPLIANCE

Subjects will be provided with dosing instructions each time study medication is dispensed. Subjects will also be instructed to bring their medication with them to every visit. Treatment compliance will be summarized by treatment for 603A and 603B.

Compliance in studies 603A, 603B, and integrated will be calculated as follows:

- Percent compliance = (number of tablets consumed / number of tablets that should have been taken) x 100.
- Number of tablets consumed is computed as in Section 9.1.
- Number of tablets should have taken = number of exposure days.
- Number of exposure days = last dose date - first dose date + 1.

If any of the bottles dispensed are not returned, the number of tablets consumed and compliance will be considered as missing. Compliance will be summarized for each period by actual treatment for safety analysis set. A separate table for overall compliance will be presented without treatment arms. A frequency summary of compliance will also be presented with the following categories: < 75%, 75-<100%,

100-120%, and > 120%.

9.3. ADVERSE EVENTS

Adverse events will be collected and recorded after a subject is enrolled in the study to the last scheduled contact. Any new serious adverse events (SAE) reported by the subject to the investigator that occur after the last scheduled contact, and are determined by the investigator to be reasonably associated with the use of the investigational product, will be included in the analysis.

For all AEs, preferred AE terms and system organ class (SOC) will be coded using terminology from the Medical Dictionary for Regulatory Activities (MedDRA), version 19.0 or above.

A treatment-emergent adverse event (TEAE) is defined as an AE that begins (or an existing condition that worsens) after the first administration of double-blind study medication in study 603A). TEAE will be summarized separately for periods: study 603A and study 603B after randomization, dependent upon in which period the event started. TEAE summary for all periods combined will include all bexagliflozin TEAEs started on or after the first dose of bexagliflozin and before the last dose of bexagliflozin.

Drug-related AEs will be considered those to be possibly, probably and definitely related to bexagliflozin administration based on the investigator's assessment.

Unless otherwise specified, AEs will be summarized by SOC and PT, with SOCs and PTs within SOCs presented in descending order of subject incidence.

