### **9.7.1 Adverse Events**

AEs will be mapped to preferred term and body system using the Medical Dictionary for Regulatory Activities (MedDRA) dictionary. AEs that begin at or after the first administration of double-blind study medication (i.e., first dose of study 603A) or existing AEs that worsen in severity after the first dose of double-blind study medication are considered treatment emergent AEs (TEAE). Treatment emergent periods will be divided into three periods: study 603A, study 603B prior to randomization, and study 603B after randomization. The number and percentage of subjects reporting TEAEs will be summarized for each treatment group by MedDRA system organ class and preferred term, for each period as well as all periods combined. Further summaries by severity and by relationship to study treatment will also be provided. Drug-related AE will be considered those to be at least possibly related to the study treatments based on the investigators assessment.

Similarly, the number and percentage of subjects reporting serious AEs, and the number and percentage of subjects reporting AEs leading to treatment discontinuation will also be summarized for each treatment group by MedDRA system organ class and preferred term.

In addition, adverse events of special interest include, but not limited to UTI, GMI, hypoglycemia, hepatotoxicity, MACE, and DKA events, will be separately summarized.

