9.3.1. Derived Data

AE onset day is calculated as (date of AE start - date of first double-blind dose of each study + 1).

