9.3.2. Data Summarization

The AE summaries will include:

- An overall summary of the number and percentage of subjects reporting any TEAEs, serious TEAEs, treatment-related TEAEs, serious treatment-related TEAE, any TEAEs leading to treatment discontinuation, any TEAEs leading to subject withdrawal and TEAEs leading to death.
- TEAEs overall and by SOC and PT
- TEAEs by severity, overall and by SOC and PT

- Serious TEAEs, overall and by system organ class and preferred term
- TEAEs by relationship to study treatment, overall and by system organ class and preferred term
- TEAEs leading to treatment discontinuation, overall and by SOC and PT
- TEAEs leading to study withdrawal, overall and by SOC and PT
- Common TEAEs. Common TEAEs are as TEAEs that occur in > 5% of the subjects in either of the treatment groups.

Except for common TEAEs, each data summary will be presented for the 603A period, for the 603B period after randomization, and for the integrated bexagliflozin treatment periods. Common TEAEs will be presented for the integrated bexagliflozin treatment period. Tables for the 603A will be summarized by treatment received in 603A and overall. The summary table for the 603B period after randomization will contain 2 layers: 1) 603B treatment, and 2) split 603B treatment by 603A treatment groups. Tables for integrated bexagliflozin treatment periods will present number and percentage of subjects with event, and exposure adjusted AE rate (i.e. rate per 100 patient years of bexagliflozin). Events will be summarized according to the actual treatment when the event starts. The denominator for percentage calculations will be the total number of subjects who receive at least one dose of the specified treatment. All subjects should have received at least one dose of bexagliflozin unless they were withdrawn from study 603A.

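### The SAP counts a worsening AE as treatment emergent but files it by event start, so worsening after the placebo-to-bexagliflozin switch can drop out of the integrated bexagliflozin AE tables

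*SAP*

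**What the plan says.** Both documents accept worsening as a route to being treatment emergent, with one reference point. In Protocol 9.7.1, "existing AEs that worsen in severity after the first dose of double-blind study medication are considered treatment emergent AEs". In SAP 9.3 a TEAE is an "AE that begins (or an existing condition that worsens) after the first administration of double-blind study medication in study 603A".

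The assignment rules use only the start of the event:

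- **Period (SAP 9.3):** "TEAE will be summarized separately for periods: study 603A and study 603B after randomization, dependent upon in which period the event started".
- **Integrated bexagliflozin set (SAP 9.3):** the combined summary will "include all bexagliflozin TEAEs started on or after the first dose of bexagliflozin and before the last dose of bexagliflozin".
- **Treatment (SAP 9.3.2):** "Events will be summarized according to the actual treatment when the event starts".
- **Onset day (SAP 9.3.1):** "AE onset day is calculated as (date of AE start - date of first double-blind dose of each study + 1". No worsening date is derived.

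SAP 12 withdraws the separate 603B run-in AE summary that the protocol had promised and relies on the integrated safety set in its place. SAP 9.3.3 keeps a run-in table for AEs of special interest, in the format of SAP 9.3.2.

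**The concern.** Everyone who enters 603B takes bexagliflozin for 12 weeks, including those who were on placebo in 603A. For those subjects the last drug-free state is the end of 603A, not Day 1. SAP 6.2.1 recognises this for measured quantities: for sequences PBB and PBP it resets the baseline to the last value before the first bexagliflozin dose, and applies that to the safety summaries by weeks of bexagliflozin treatment. AEs get no matching reset.

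The definition of emergence and the filing rules therefore use different tests. An AE that is mild on placebo and becomes worse after the switch has worsened on the drug, yet the filing rules look only at when it began. At stake is the completeness of the integrated bexagliflozin AE tables and of their exposure-adjusted rates. SAP 12 makes these the main general summary of what happens in the 603B run-in.

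**Working it through.** The plan gives no figure to reproduce. The check follows one case through the rules.

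**Case.** A subject is randomized to placebo in 603A. An AE starts during 603A, is still present at visit 6, and increases in severity during the 603B run-in on bexagliflozin. It is kept as one AE record with one start date.

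| Output | Rule applied | Result |
|---|---|---|
| 603A AE tables | Started in 603A, on placebo | Counted under placebo |
| 603B post-randomization AE tables | Did not start in that period | Not counted |
| General 603B run-in AE table | Dropped by SAP 12 | No table |
| Run-in table of AEs of special interest | SAP 9.3.2 format, treatment at event start | Not counted as a bexagliflozin event |
| Integrated bexagliflozin tables and rate per 100 patient-years | Started before the first bexagliflozin dose | Not counted |
| Listing of all AEs (SAP 9.3.2) | No start restriction | Shown |

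**Severity and discontinuation.** SAP 9.3.2 tabulates a subject's most severe event in the period, but has no rule for a grade reached after the period ends. With one record per AE, a grade or a discontinuation reached on bexagliflozin could be shown under the 603A treatment, here placebo.

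**The same case with the worsening as a new record.** The new record starts after the first bexagliflozin dose. It enters the integrated tables, and the gap closes. The outcome turns on a recording convention that neither document states.

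**Number of subjects who switch.** Inputs from Protocol 9.2 and SAP 3.7: 680 randomized, 1:1, with about 8% lost in the first 12 weeks.

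- 680 × (1 − 0.08) = 625.6, the plan's 626.
- 626 / 2 = 313 planned placebo subjects who start bexagliflozin at visit 6.

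**Number affected.** The documents give neither the share with an ongoing AE at visit 6 nor the share of those that worsen, so this cannot be computed. For scale only, assume 10% to 20% have an ongoing AE and 10% of those worsen:

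- 313 × 0.10 × 0.10 = 3.1 subjects
- 313 × 0.20 × 0.10 = 6.3 subjects

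Planned bexagliflozin exposure is about 680 / 2 + 313 = 653 subjects, so this would be 3.1 / 653 = 0.5% to 6.3 / 653 = 1.0%. Both assumed rates are without source, and the conclusion does not rest on them.

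**The case against.** The strongest reply is that attribution by treatment at onset is a stated and coherent rule, and that the harm depends on a convention held in papers not supplied here (the CRF, its completion guidance, the table shells). One can also read the period rule so that, for a TEAE defined by worsening, the worsening is what started. The dependence stands, and the conclusion is conditional on it. The alternative reading is possible, but SAP 9.3.1 works from the AE start date alone, and nothing in the SAP supplies a date for the worsening.

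A reader might infer three stronger things that the documents do not support.

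- **That the 603A placebo comparison is biased.** It is not, as regards incidence. An AE that began on 603A placebo is a true placebo-period event. The change proposed here would leave it there and add a bexagliflozin event. Only the severity or discontinuation shown could shift, and only if one record is overwritten. After the second randomization, the start rule applies equally to both randomized arms.
- **That such events vanish, or that a pre-study condition worsening in 603B falls in no table.** The AE listings still show the event, and a laboratory change can appear in the shift tables of SAP 9.4. Pre-study conditions are held in medical history (SAP 7.4), so their worsening would most naturally be entered as a new AE with its own start date. The exception is narrow: an AE opened between consent and first dose and kept on one record.
- **That the error always favours the drug.** An AE that starts on bexagliflozin and worsens on withdrawal placebo remains a bexagliflozin event in the integrated table.

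**Conclusion.** The point holds in a limited form. The inclusion rule for the integrated set conflicts with the SAP's own TEAE definition: worsening makes an event treatment emergent, but no rule brings a worsening on bexagliflozin into a bexagliflozin table when the event began on placebo. The loss of the general run-in AE table leaves no other general summary to catch it.

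The consequence is a possible under-count in the integrated bexagliflozin AE tables and rates, together with a possible display of bexagliflozin-period severity or discontinuation under 603A treatment. It rests on one assumption that the documents leave open, namely that a worsening stays on the record opened at onset. About 313 planned subjects are exposed to the gap. The number of affected events is unknown and may be small.

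**What to change.** In SAP 9.3 and 9.3.2:

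1. Define TEAE separately for 603A, the 603B run-in and the 603B withdrawal period as onset, or increase in severity, on or after the first dose of that period, judged against the state just before that dose. For the integrated set, use the first bexagliflozin dose as the reference.
2. Assign each event to the treatment being taken at the date of onset or of worsening.
3. State that a worsening carries its own date, either as a new AE record or as a dated change of grade. SAP 10 describes the interim analysis as already done, so use data queries for AEs already collected.

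The cost is some extra programming and querying. Bexagliflozin counts may rise slightly. No endpoint, sample size or clinical procedure changes.
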